10.3 Randomization

Following determination of full study eligibility via screening, and completion of baseline assessments, participants will be randomly assigned to one of the two conditions (rTMS or sham) for 8 weeks. Random assignment will be on a 1:1 ratio to one of the two conditions. Randomization will be stratified by study site, presence/absence of current major depressive episode, and primary CUD or MUD designation. The randomization procedure will be conducted centrally through the CTN DSC, and randomization assignments will not be conveyed to local research staff or participants. The randomization schedule will be programmed into the rTMS machine so that neither the participant nor the rTMS Operator or research staff knows what condition was assigned. The DSC statistician will generate the randomization schedule using balanced blocks of varying sizes within strata to ensure lack of predictability along with relative equality of assignments across treatment groups. The DSC statistician will review randomization data on a regular basis to ensure that the scheme is being implemented according to plan. A randomization slot, once used, will not be re-allocated, due to the intent-to-treat nature of the study.

10.4 Treatment/Intervention

Prior to receiving the first active/sham rTMS intervention, the participant will meet with the Advanced TMS Operator to determine the participant's motor threshold (MT). See Section 11.2 for description. Once the participant motor threshold has been determined, participants will receive either active rTMS or sham rTMS treatment as determined at Randomization

10.4.1 rTMS and Sham

Either repetitive transcranial magnetic stimulation (rTMS) or sham (control) will be delivered to study participants during treatment sessions after exposure to approximately 5 minutes of imaginal (script-based) and visual methamphetamine (for MUD participants) or cocaine-related cues (for CUD participants). The delivery of active versus sham intervention will be controlled by a dual active/sham coil. Administration of active versus sham rTMS will be determined by the computer controlling the coil; randomization status will have been entered into files used by the computer during DSC randomization. With this procedure, rTMS Operators and other research staff will be kept blind to participants' condition assignments. The coil will be placed to stimulate the left DLPFC. Section 11 provides specific rTMS parameters and considerations.

Prior to each rTMS/sham session, cues designed to activate craving will be presented. At the first session, participants will complete a triggers worksheet. At each subsequent session, participants will be presented with their completed worksheet and asked to imagine that they are re-experiencing a time when they were tempted to use and to imagine the pleasure they would experience following use. This will continue for approximately one minute, then a set of slides with photographs of cue situations and objects will be presented for approximately two minutes. The post-cue craving assessment will be completed and the rTMS/sham session will begin afterwards. Craving and ability to resist use will also be assessed upon completion of the rTMS/sham treatment session.

Research staff will maintain study visit logs throughout the study period to monitor intervention adherence. Research staff will manage assessment and intervention appointment scheduling. Treatment sessions will be offered daily during the work week, with flexibility to allow occasional evening and weekend appointments, as well as multiple treatment sessions in one day (maximum 2 per day, 5 per study week).

10.4.2 Other Study Procedures:

Actigraphy: After randomization, participants will be issued an ActiGraph to assess daily sleep quality during weeks 1-8. The ActiGraph GT9X Link wristband device is an FDA cleared device. Information obtained from the device includes, but is not limited to, sleep latency, sleep duration, and intervals of waking during the sleep period. Participants will be provided with the device and necessary accessories for wear and battery charging. Research staff will download data from the device once a week. The participant will return the device at the end of treatment visit.

Electroencephalography (EEG): If available at the study site, EEG will be obtained after randomization and again at week 4, to explore the potential for EEG to be used as a biomarker of treatment response. The week 4 EEG will only be obtained for those participants for whom the EEG was conducted at randomization. Participants will wear a cap that will fit snugly on their head for this procedure. It is a quick and well-tolerated procedure to measure the summed electric potential of the brain measured at the scalp. Resting-state EEG will be recorded (5 minutes resting eyes open, 5 minutes resting eyes closed). The post-hoc analyses of the EEG provide a whole-brain connectomic profile (Toll, et al., 2020) before and after the course of treatment, revealing changes in functional brain connectivity. For this study, EEG will be performed at randomization and again at week 4 at study sites equipped to perform EEG. These analyses are considered exploratory. The fronto-parietal control network is known to function atypically in CUD and MUD as pursuit of the addictive substance sabotages executive functioning (Stewart et al, 2016). Additionally, longitudinal EEG recorded in adults at onset of abstinence from cocaine produced activation topographies consistent with the salience network which is integral to cue-related processing (Parvaz et al., 2016). Having established that specific functional networks are known to be atypically connected in addiction disorders and that resting-state EEG can resolve these networks' connectivity, an excellent opportunity presents to explore the diagnostic potential of EEG in CUD/MUD and its ability to predict therapeutic response to rTMS.

10.4.3 Safety Monitoring of Intervention

Intervention tolerability and effects will be systematically assessed before and after each treatment. This includes assessing for factors that impact seizure threshold (e.g., increased stimulant use). Retesting of MT may occur as outlined in the rTMS intervention section below. Participants will be encouraged to contact research staff between visits to address any immediate concerns regarding adverse events and medication changes; however, information on adverse events and medication changes also will be collected during assessment and intervention appointments. The Study Medical Clinician will meet with the participant before, during, or after any study intervention if the rTMS Operator or participant is concerned for the potential of a serious adverse event, including seizure. If suspected seizure occurs during study intervention, the Study Medical Clinician will arrange for the participant to be transferred to local emergency

room for further management. In the event of a seizure during the study, the participant will be discontinued from further study intervention.

10.4.4 Cognitive-Behavioral Educational Intervention

Participants in both conditions (rTMS and sham) will also participate in a CBT for SUD educational intervention that will be delivered via a mobile application platform developed and managed by DynamiCare Health. Twenty (20) self-guided modules will deliver evidence-based CBT and motivational strategies and educational therapeutic content to participants. Participants will be asked to complete 2-3 modules per week during the treatment phase (rTMS or sham). Modules are brief (less than 30 minutes to complete), contain both didactic and interactive content (i.e., activities to reinforce didactic content), are available anytime, and may be completed in single or multiple “sessions.” Modules may be completed in any order. Participation will be tracked but will not be incentivized. Session topics and a brief summary of content are provided in Table 4 below.

Table 4: Cognitive Behavioral Educational Session Topics

Module Title	Content Summary
Hijacking the Brain: Disease of Addiction	Signs of addiction: loss of control and Overview of disease of addiction
Triggers (learning about triggers): Part 1	Identifying personal triggers and reaction (positive and negative) to them
Triggers (practice scenarios): Part 2	Practice 3 scenarios identifying triggers, and subsequent reaction/behavior
Healthy Coping Skills: Part 1	Planning for encountering triggers and introduction to healthy coping options
Healthy Coping Skills: Part 2	Avoiding triggers and managing/coping with unavoidable triggers
Justification	Identification of own justifications for substance use
Relapse Prevention Plan: Part 1	Planning for triggers, implementing healthy coping plan, attaining sober support
Relapse Prevention Plan: Part 2	Implementing a healthy coping plan for triggers
Relapse Prevention Plan: Part 3	Identifying sober support and putting relapse prevention plan into practice
Relapse Prevention Tips: Part 1	Avoiding relapse: Skills training for HALT, urge surfing, and setting healthy boundaries
Relapse Prevention Tips: Part 2	Reviewing HALT, urge surfing, and boundary setting
Building Discrepancy – Decision Making Skills	Focus on evaluating & responding vs. reacting; Differentiating between healthy vs. unhealthy coping
Cognitive Behavioral Model: Part 1	Introducing tripartite model and evaluating thoughts for cognitive distortions
Cognitive Behavioral Model: Part 2	Reviewing CBT model and introducing reframing

Module Title	Content Summary
Rational vs. Irrational Thoughts	Identifying irrational thoughts based in fear rather than fact
Self-Care Assessment	Building a healthy lifestyle via activities that promote physical, mental & emotional health
Dealing with Stressors	Defining stress and identifying warning signs of chronic stress (e.g., fatigue)
Mindfulness	Introducing core mindfulness components of awareness and acceptance; Mindfulness practice exercise
Grounding Techniques	Teaching techniques including: (1) Refocusing on present moment during uncomfortable feelings, distressing memories, triggers, and (2) 5-4-3-2-1 exercise and practice
Using Your Strengths	Identifying personal strengths and their role in achieving personal goals

10.4.5 Clinical Deterioration “Rescue” Plan

A clinical deterioration “rescue” plan will be in place for participants who experience psychiatric or SUD deterioration during the study. Symptoms will be monitored closely throughout the trial to assess for deterioration (e.g., using the suicidality items on the Concise Health Risk Tracking questionnaire). Those who endorse suicidal thoughts or intent on the CHRT-SR will be further assessed on the CHRT-Clinician Rated assessment. Appropriate intervention will be arranged for any participant demonstrating gross clinical deterioration or suicide risk. The rescue measures will include referral for appropriate clinical intervention, including removal from the study and referral to SUD treatment should the participant demonstrate increasing substance use.

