10.6 Collection of Biospecimens

Urine samples will be collected from all participants for urine drug screen (UDS), the main efficacy outcome measure of the study. This will occur at screening, randomization, during each treatment session prior to beginning the intervention, during the end of treatment visit and follow-up assessments (UDS will be omitted if follow-up visits are performed remotely). A newly positive UDS will result in recalibration of the motor threshold before rTMS delivery. For females of child-bearing potential, a urine pregnancy test will be administered. Results of the urine pregnancy test will be obtained prior to performing the UDS, at screening, randomization, at weeks 4 and 8 of treatment and at any other time a woman reports she might be pregnant. A positive pregnancy test post-randomization will result in the cessation of rTMS/sham treatment. The research staff will follow the participant until an outcome of the pregnancy is known and reported.

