10.7 Premature Withdrawal of Participants

All participants will be followed for the duration of their participation in the study unless they withdraw consent, die, or the investigator or sponsor decides to discontinue their enrollment for any reason. Reasons for the investigator or sponsor terminating a participant from the study may include, but are not limited to, the participant becoming a threat to self or others, the participant acquiring an exclusionary condition, lack of funding, or Data and Safety Monitoring Board (DSMB) early termination of the study for safety reasons.

Should participants be lost to follow-up, efforts to pursue participant locator information such as multiple contact options (e.g., phone, address, email, social media) and collateral contact information will be maintained. At any time, participants may decide that they no longer wish to continue to participate in the study.

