12.2.7 Study Completion Form

This form tracks the participant's status in the study. It is completed at the week 16 follow-up visit, or once the week 16 follow-up visit window lapses for participants who do not complete this final follow-up. If the participant withdraws consent, dies or is removed from the study per judgement of research staff, this form will be completed at the time of termination from the study. This form is used in data analyses to address variables such as treatment retention and completion. This form also provides a location for the site PI attestation of review of all study data.

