The site Medical Clinician must apply his/her clinical judgment to determine whether or not an adverse event is of sufficient severity to require that the participant be withdrawn from further study intervention. The site Medical Clinician should consult with the site Principal Investigator, the Lead Investigator and/or Safety Monitor/Medical Monitor as needed. If necessary, a site Medical Clinician may suspend any trial treatments and institute the necessary medical therapy

to protect a participant from any immediate danger. A participant may also voluntarily withdraw from treatment due to what he/she perceives as an intolerable adverse event or for any other reason. If voluntary withdrawal is requested, the participant will be asked to complete an end of rTMS/sham visit to assure safety and to document outcomes and will be given recommendations for medical care and/or referrals to treatment, as necessary.

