Local Node site visit reports are sent to those entities required of them by the Lead Investigative team, generally including the Lead Investigator, site Principal Investigator, Node PI and a CCC representative, usually the Clinical Study Manager for the study.

E. Management of Risks to Participants Confidentiality

Confidentiality of participant records will be secured by the use of study codes for identifying participants on CRFs, and secure storage of any documents that have participant identifiers on site, as well as secure computing procedures for entering and transferring electronic data. The documents or logs linking the study codes with the study participant on site will be kept locked separately from the study files and the medical records. No identifying information will be disclosed in reports, publications or presentations.

Information Meeting Reporting Requirements

The consent form will specifically state the types of information that are required for reporting and that the information will be reported as required. These include suspected or known sexual or physical abuse of a child or elders, or threatened violence to self and/or others.

Participant Protection

The site's study clinician will evaluate all pertinent screening and randomization assessments prior to participant randomization to ensure that the participant is eligible and safe to enter the study. AEs and concomitant medications will be assessed and documented at each study visit. Individuals who experience an AE that compromises safe participation in a study will be discontinued from further rTMS intervention and provided referrals for other treatment or to specialized care. Study personnel will request that the participant complete an end-of- intervention visit to assure safety and to document end-of-intervention outcomes.

Pregnancy

A positive pregnancy test post-randomization will result in the cessation of rTMS/sham treatment. The research staff will follow the participant until an outcome of the pregnancy is known and reported.

Study Specific Risks

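### The rescue plan lists removal from the study, not only stopping sessions and referral, when a deteriorating participant's use increases; data then stop for a reason related to the secondary outcome, with a probably negligible to small effect

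*Protocol*

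**What the plan says.** **The rescue rule.** Protocol 10.4.5 sets the scope: "Appropriate intervention will be arranged for any participant demonstrating gross clinical deterioration or suicide risk". It then lists the rescue measures, "including removal from the study and referral to SUD treatment should the participant demonstrate increasing substance use". No threshold for increasing use is given.

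**What removal means.** Section 10.7 follows everyone for the full study "unless they withdraw consent, die, or the investigator or sponsor decides to discontinue their enrollment for any reason". Section 12.2.7 says that for someone "removed from the study per judgement of research staff, this form will be completed at the time of termination from the study", not at Week 16. The Table 6 footnote adds an EOT assessment for early withdrawals, and SAP 7.4 lets that UDS count toward a study week.

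**Other safety events.** These stop the intervention only:
- Seizure (10.4.3): "In the event of a seizure during the study, the participant will be discontinued from further study intervention".
- Pregnancy (10.6): "A positive pregnancy test post-randomization will result in the cessation of rTMS/sham treatment".
- Adverse events (Appendix A): the clinician judges whether severity is enough "to require that the participant be withdrawn from further study intervention".
- Adverse events that make participation unsafe (Appendix B): these individuals "will be discontinued from further rTMS intervention and provided referrals for other treatment or to specialized care".

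Section 6.1 foresees a participant entering formal treatment while staying in the study, with time in treatment recorded. Section 10.8 continues follow-up for those who stop the intervention but remain. SAP 3.1.3 analyses everyone randomized, whether or not they withdrew from treatment.

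**Analysis.** The main model uses all available weekly UDS under missing at random, without imputation (Protocol 15.6, SAP 7.9). SAP 7.9 plans four sensitivity analyses: missing as negative, missing as positive, TLFB-based imputation, and multiple imputation that treats dropout as missing not at random with sham-based values.

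**The concern.** The secondary outcome is the weekly UDS result for the primary stimulant. A participant removed because use is rising leaves the data for a reason related to that outcome. If this happens more in one arm, the comparison is made on selectively incomplete data. Whether the main model copes depends on whether the trigger was a recorded UDS, which the model contains, or self-report and clinical judgement, which it does not. Weekly CHRT-SR monitoring and the Week 12 and 16 visits also stop, in people already judged to be deteriorating. Section 6.1 shows that referral does not require leaving the study, so the loss is avoidable.

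**Working it through.** **1. Is the loss real on the text?** Removal (10.4.5) is an investigator's decision to end enrollment (10.7), and the completion form closes then (12.2.7). Section 10.8 covers only those who remain in the study. Nothing continues UDS, TLFB or Weeks 12 and 16 after removal, apart from the exit EOT assessment. If removal follows the UDS of week 3, 4, 5 or 6, the weeks lost are 5, 4, 3 or 2, a mean of 3.5 of 8. The mean is 2.5 if the EOT UDS fills one.

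**2. The plan's own power figures.** Inputs from Protocol 15.2.2: N = 80, 8 weekly UDS, sham probability 0.36, random-intercept SD 1.81 (ICC 0.5) or 1.05 (ICC 0.25). A random-intercept logistic model with treatment as the only fixed effect gave these powers, all within 2 points of Table 8:
- OR 4, ICC 0.5: 84.8% (stated 86%)
- OR 2, ICC 0.5: 33.1% (35%)
- OR 2, ICC 0.25: 66.2% (67%)
- OR 3, ICC 0.25: 95.0% (96%)

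**3. Effect of removal at sham probability 0.36.** All worsening and removal rates are assumptions. Setup: underlying OR 2, SD 1.81, 60,000 per arm, 4 replicates. Worsening starts in a uniformly chosen week from 3 to 6, with P(negative) = 0.05 from then on, and removal follows that week's UDS. The model has treatment and categorical week. Monte Carlo SE of each OR is about 0.01 or less. For scale, 35% power at N = 80 gives SE(log OR) = ln 2 / (1.96 − 0.385) = 0.44.

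| Sham/active removed | OR, data kept | OR, removed | ln(kept/removed) | Size in SE |
|---|---|---|---|---|
| 5%/2.5% (2 v 1 of 40) | 2.05 | 2.02 | 0.015 | 0.03 |
| 5%/5% | 1.97 | 1.99 | −0.010 | 0.02 |
| 10%/5% | 2.09 | 2.03 | 0.029 | 0.07 |
| 20%/10% | 2.19 | 2.06 | 0.061 | 0.14 |
| 20%/20% | 1.87 | 1.92 | −0.026 | 0.06 |
| 40%/20% | 2.39 | 2.12 | 0.120 | 0.27 |
| 10%/20% | 1.66 | 1.84 | −0.103 | 0.23 |
| 10%/30% | 1.41 | 1.71 | −0.193 | 0.44 |

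The sign follows the arm that worsens more. It also depends on use after referral. At 20%/10%, if P(negative) moves to 0.20, 0.36 or 0.50, the kept OR is 2.05, 1.94 or 1.86, against 2.06 removed.

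**4. A very low negative rate.** SAP Table 5 does not print the observed sham rate. Moving it by −0.025, 0 and +0.025 takes power from 25% to 42% to 54% (n = 50, OR 2). Protocol Table 8 gives 33%, 35% and 33% at 0.26, 0.36 and 0.46 (N = 80, ICC 0.5). That steepness, and the lack of UDS variability reported in SAP 7.10, point to a low rate. With an assumed 0.055 and SD 0.5 (kept versus removed):
- 5%/2.5%: 2.02 v 2.01 if worsened P = 0.02; 1.99 v 2.00 if 0.05
- 20%/10%: 2.06 v 2.01 if P = 0.02; 1.96 v 1.99 if 0.05
- 10%/30%: 1.75 v 1.93 (P = 0.02)

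With 42% power at n = 50, SE = ln 2 / (1.96 − 0.202) = 0.39. The first shifts are then under 0.02 SE. The last is ln(1.93/1.75)/0.39 = 0.25 SE.

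**5. A different removal rule.** Assume removal with probability 0.15 in each week that completes two consecutive positive UDS (OR 4, ICC 0.5). The median OR is 3.99 if the triggering UDS is recorded and 3.71 if it is not, against 4.06 with no removal. Raw percent negative rises from 41% to 44–47% in sham and from 63% to 65–67% in active. This matters if SAP 7.10.1 falls back to summary percentages alone.

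**6. Do the planned analyses recover it?** With no other dropout, missing-as-positive gives 2.24 at 20%/10%. That is close to the kept 2.19 if use stays high, but not to 1.94 if P(negative) recovers to 0.36. TLFB-based imputation needs TLFB, which also stops. Sham-based imputation draws on observed sham values and does not model deterioration; SAP 7.10.2 allows multiple imputation to go unreported.

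**The case against.** The strongest reply is that this is a narrow safety provision with no demonstrated effect. The trigger sits under gross deterioration or suicide risk, removal is one listed measure, and nothing makes it automatic. Entrants use on at least 10 of 30 days, and the UDS looks back roughly 3 days. At a low negative rate, rising use therefore mostly turns one positive result into another. The SAP recognises that use after dropout may differ and plans for it. UDS after referral would mix in outside treatment, which exclusion criterion 14 says would interfere with outcome assessment. Weeks 12 and 16 do not enter the secondary outcome, and remote visits have no UDS.

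Most of this stands, and it limits the point to a cheap improvement. It does not remove the textual gap: seizure, pregnancy and unsafe adverse events stop sessions only, and 6.1 already accepts outside treatment and records it. If removal was meant only as stopping sessions, the rewording is a clarification.

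A reader might infer that every rise in use forces removal, or that missing at random must fail. The documents support neither: the scope is narrower, and if recorded UDS drive removal the assumption can hold.

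**Conclusion.** Followed as written, 10.4.5 ends data collection for a reason related to the secondary outcome, where the rest of the protocol would stop sessions and keep observing. The removal frequency is unknown. The effect on the secondary OR is probably negligible to small: about 0.03 SE for 2 versus 1 removals of 40 per arm, and near nil at a very low negative rate when removals are few. It reached 0.44 SE only when removals were assumed three times as common in the active arm, which nothing in the documents suggests. All of this rests on assumed removal rates, an assumed probability after worsening and, for the low-rate case, an inferred sham rate.

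A reader might infer that the secondary result is biased for or against rTMS. The documents do not support that: the direction depends on which arm worsens more and on use after referral, and neither is given. The primary feasibility outcome has no missing data and is unaffected.

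**What to change.** Replace the last sentence of 10.4.5 with:

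> Rescue measures may include stopping rTMS/sham sessions and referral for appropriate clinical intervention, including SUD treatment if substance use increases. Increasing substance use alone is not a reason to end study participation; weekly UDS and TLFB and the EOT, Week 12 and Week 16 visits continue unless the participant withdraws consent or is discontinued on a safety ground under Section 10.7.

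Add to 10.7 that increasing use, or referral to SUD treatment, is not by itself a ground for discontinuing enrollment. Without this, the open-ended discretion in 10.7 would still permit the same removal. The safety grounds there, such as threat to self or others, stay.

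The cost is two short text changes plus a few extra visits and urine tests for participants who stop sessions. UDS after referral will partly reflect outside treatment, so it should be read with the time in treatment recorded under 6.1. The change cannot recover data already locked. It applies to continuing use of the protocol and to the larger trial this pilot is meant to inform. For the present data, a by-arm count of such removals from the existing completion and end-of-treatment forms is optional.
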